8.0 Human Subjects Considerations

8.1 Ethical Review

The study protocol, informed consent forms, and other requested documents — and any subsequent modifications — will be reviewed by the Human Sciences Research Council Research Ethics Committee in South Africa, and the Institutional Review Board at the University of California, San Francisco. Subsequent to initial review and approval, the responsible IRBs/ECs will review the study at least annually.

Each site Investigator will make safety and progress reports to the IRBs/ECs at least annually, and within three months after study termination or completion. These reports will include the total number of participants enrolled in the study, the number of participants who completed the study, all changes in the research activity, all SAEs, and all unanticipated problems involving risks to human subjects or others.

The results of all DSMB reviews of the study also will be provided to the IRBs/ECs.

8.2 Informed Consent

Consent for participation in pilot RCT. Couples will arrive together for their appointments which will begin with the informed consent process. Partners will be consented individually in a private interview room by a gender-matched interviewer in the local language. The consent process will cover topics on the purpose of the study, potential risks and benefits, how confidentiality will be

Couple-Based Motivational Interviewing with Mobile Breathalyzers to Reduce Alcohol Use in South Africa

ensured, voluntary participation, the funding agency and study investigators, and contact information for the study PIs. The study's consent form will be read and explained to them by the interviewer. A detailed description of the study procedures will be included. The consent form will include the information that they have the right to refuse or withdraw from participation at any time. The consent form will provide detailed descriptions of the expectations of being a participant in either of the study groups, along with the accompanying potential risks and benefits of each. Information will be presented on randomization, following procedures used to describe randomization in our prior studies in the region. A paper version of the information sheet will be offered to participants with the goals of the research, the study procedures, and the names and contact info for the principal investigators will also be provided, and a contact number for the local PI. The consent process will also ask respondents if they agree to be contacted to participate in additional study activities beyond what is required for the proposed study and whether it is acceptable to track them at their homes if phone calls do not go through.

Consent for biomarker collection. The main consent form will include consent for obtaining biomarker specimens, detailing the appropriate risks, procedures involved, and any benefits. Respondents will be informed of the risks/benefits and that the results of the HIV and alcohol biomarker (PEth) tests will not be made available to them.

Consent for qualitative data collection. For the qualitative phases (FGDs for Aim 1 and exit interviews for Aim 3), we will use separate consent forms. For the FGDs, the process will inform respondents that others in the group will learn of their HIV status (although all group members will be HIV+) and confidentiality cannot be assured so they must choose carefully the information that is shared with other group members.

Electronic signatures for consent will be obtained for all participants; for those who cannot write their names, they will place an "X," their thumbprint, or their mark on the consent form. The interviewer and an impartial witness, who the participants knows and trusts, will also sign the consent form. All consent forms will be translated into isiZulu (the predominant local language) and then back translated by a separate individual in order to ensure proper translation. Given the high levels of illiteracy in this context, study staff will read the written version of the consent form and test for an understanding at the end with a series of simple questions (e.g., "can you tell me what will happen if you agree to participate in the study?"). Respondents will be offered a copy of the consent form in isiZulu (or in English, if preferred). All consent forms will be approved by the IRBs of both UCSF and HSRC in South Africa.

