3.0 Study Population

3.1. Couple Eligibility

Inclusion criteria:

- (1) In a primary relationship for at least six months
- (2) Aged 18-49
- (3) Have at least one partner (the “index patient”) with a positive AUDIT-C screen (score of 4 for men and 3 for women; prior 3 months) and on ART for at least six months (a time when alcohol use is found to rebound) who has disclosed their HIV status to their partner in the study
- (4) Both partners separately agree to participate in the study for the couple to be enrolled.

Exclusion criteria:

We will exclude participants with an AUDIT-C score greater than 12, indicating risk of severe alcohol use disorder. Participants with severe drinking issues may not benefit from a brief counseling-based intervention and may need more intensive treatment than our study can provide.

Considering the intervention has a technology component and there may be a difference in acceptability between younger/older participants, we will impose an upper age limit of 49 (an age in which smartphone ownership and internet connectivity drops off in South Africa). We will not exclude those without phones or with incompatible phones to avoid widening the digital divide and excluding those who could really benefit from the intervention. We have budgeted for

Couple-Based Motivational Interviewing with Mobile Breathalyzers to Reduce Alcohol Use in South Africa

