3.2. Recruitment Process

Aim 1: For the two FGDs with couples (3-4 couples per group), we will recruit couples using procedures from our prior studies with couples in South Africa and Malawi. A team of recruiters will approach index patients at HIV clinics while waiting to attend appointments. We will announce the study during the daily health information talks in the waiting rooms and interested patients can approach the recruiters. If the patient is interested and eligible, we will provide them with a study information card to give their primary partner and will set up a phone appointment to screen the partner. If both partners are interested and eligible, the couple will be invited for a secondary screening to verify that the partnership is legitimate (e.g., confirming partner names, relationship length, etc.). To ensure we capture primary partnerships, both partners will be asked, "Of all your romantic partners, who are you the closest with?" Screenings will be interviewer-administered using tablet devices. If the couple remains eligible, both partners will provide written informed consent and be invited to participate. Partners will be consented separately to ensure a lack of coercion. Couples who are ineligible will be informed that they are ineligible but will not be given a specific reason why (i.e. which eligibility criteria they did not meet). Recruiters may deflect questions about eligibility by saying, "the computer program determines eligibility but does not provide a specific reason." Similarly, couples who are ineligible because one or the other does not want to participate will not be informed that this is the reason for ineligibility to avoid disclosing each partner's decision to provide consent.

Couple-Based Motivational Interviewing with Mobile Breathalyzers to Reduce Alcohol Use in South Africa

Couples may also be identified from previous or current studies who have consented to be contacted for other research studies, and through our community partners and associated HIV testing/care services.

For the three FGDs with stakeholders (6-8 per group), which will consist of HIV care providers (nurses, clinic volunteers, clinicians), community representatives and religious leaders who interact with couples who drink, and alcohol vendors (e.g., shebeen owners, local brewers), we will recruit them using our professional networks in this region of KZN.

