by requesting clinical files from patients' HIV clinic. Participants will be asked to bring their clinic cards to study visits, which contain identifiers that can be used to look up HIV test results.

5.13 Blood samples. At screening, we will obtain consent to confirm HIV status for all participants who report being positive using a point-of-care test. We will have results in 10-15 minutes. We will base eligibility on the result of this test. We will only test potential participants who report living with HIV. We will not return test results. ***At the two-month follow-up visit, we will collect blood samples via finger pricks for testing using DBS cards. Participants who are heavy drinkers will be tested for PEth. Participants who are heavy drinkers and living with HIV will have their viral load tested.*** PEth is 95% sensitive and 73% specific for detecting heavy drinking in the past 21 days and is highly correlated with number of drinking days among PLWH in SSA. PEth samples will be processed at the United States Drug Testing Laboratories using liquid chromatography tandem mass spectrometry. PEth samples on DBS cards will be stored at the HSRC research center until they can be batch transported to the US laboratory. PEth results will be reported as positive/negative and in ng/ml. Viral load DBS samples will be processed at the Universal Pathology Laboratory (UPL) in South Africa or an HPTN Network Laboratory certified laboratory facility. Viral load DBS samples will be processed using the Aptima HIV-1 Quant Dx Assay (DBS supplement) with a lower limit of detection of 30 copies/ml. In line with standard clinical practice in South Africa, less than 1000 copies/ml will be the threshold for viral suppression.

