8.3 Risks

This study is considered minimal risk. However, participation requires at least one partner to be HIV+ and thus respondents may be identifiable to others in the community by their participation in the study. The risks associated with knowledge of a respondent's HIV+ status in the community include social stigma (e.g., rejection, isolation) and discrimination (e.g., loss of employment or status in the community). The potential risks of the study can be grouped into five categories: 1) loss of confidentiality; 2) loss of privacy; 3) couple tension, conflict and/or violence, and coercion; 4) discomfort or distress as a result of the personal and sensitive nature of the interviews or intervention sessions on alcohol, relationship dynamics, and violence; 5)

Couple-Based Motivational Interviewing with Mobile Breathalyzers to Reduce Alcohol Use in South Africa

risks associated with finger pricks to collect blood samples for viral load and alcohol biomarkers (PEth); and 6) risk of COVID-19 infection.

The intervention may not be appropriate for couples experiencing severe current IPV. We will exclude couples in which one or both members report concerns about their safety or report experiencing or perpetrating severe IPV in the prior 3 months. IPV measures will be adapted WHO measure for South Africa, which assesses physical, sexual, and emotional violence, and determines whether it is mild, moderate or severe. This approach was chosen to minimize exacerbation of potentially volatile situations while participating in a relationship-focused intervention. Given that we are not excluding couples based on ever experiencing severe IPV, and including those couples reporting any mild- to moderate IPV, we believe that this balances sample generalizability with participant safety.

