8.3.1. Minimizing risks

We will handle risks associated with couples research by following similar procedures from our team's prior work with couples in southern Africa. Any risks to respondents that stem from

Couple-Based Motivational Interviewing with Mobile Breathalyzers to Reduce Alcohol Use in South Africa

participation in the intervention, assessment visits, exit interviews, or focus group discussions will be minimized by: 1) training of staff in the ethical conduct of research; 2) training of staff in issues specifically pertaining to couples in this setting (i.e., potential for couple tension/conflict/violence, or coercion); and 3) close monitoring of any adverse events with appropriate IRB reporting; and 4) referrals to professional or community agencies providing mental health (including alcohol use disorders) or other appropriate services, when necessary. Refresher trainings on ethical procedures will be held as needed and ongoing adherence to all ethical practices will be closely monitored by the Research Manager and site PI.

During the screening process, we will have established procedures in place for ensuring that HIV+ individuals have verbally disclosed their HIV status to their primary partners in order to minimize risk associated with unintended disclosure (e.g., distress, conflict or arguments, break-ups, violence). If we cannot establish that disclosure has occurred, the screening process will be terminated due to ineligibility. We will consider HIV status disclosure to have occurred from the patient to their partner only if verified by the partner. If both partners are HIV-positive, both partners will be required to have disclosed to the other. Should the situation arise where we identify that HIV+ individuals have not disclosed their HIV status to their partner, we will have resources available (e.g., study HIV counselors) and referral pathways in place. Screening will be an interactive process and study staff will pause and check for understanding of all eligibility criteria.

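### The description of focus-group consent says every group member is HIV-positive, but the eligibility rules require this of only one partner per couple

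*Combined protocol and SAP*

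**What the plan says.** Section 8.2, in the paragraph on consent for qualitative data collection, says that FGD respondents will be informed that "others in the group will learn of their HIV status (although all group members will be HIV" (the source continues with a plus sign and closes the bracket). The qualifier at issue is the part in brackets, "although all group members will be HIV". The same sentence adds that confidentiality cannot be guaranteed and that people should take care over what they share.

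The text on who may take part is different:

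- **Section 3.1, inclusion criterion 3.** At least one partner, called the index patient, must screen positive for heavy drinking "and on ART for at least six months (a time when alcohol use is found to rebound" and must have disclosed to the partner. No criterion sets the other partner's HIV status.
- **Section 8.3.** "participation requires at least one partner to be HIV" (again followed by a plus sign).
- **Section 8.3.1.** "If both partners are HIV-positive, both partners will be required to have disclosed to the other".
- **Section 5.13.** "We will only test potential participants who report living with HIV".
- **Section 3.2, Aim 1.** "For the two FGDs with couples (3-4 couples per group"), recruiters approach index patients at HIV clinics and then "will set up a phone appointment to screen the partner". Neither this text nor Section 5.1 states an HIV requirement for the partner.

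**The concern.** The qualifier presents a shared HIV status as mitigation of the disclosure that has just been announced. Someone deciding whether to join, and what to say, could reasonably weigh a room made up entirely of people with the same status differently from a mixed room. If the room may be mixed, the qualifier understates the risk at the moment of decision.

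The protocol itself treats this risk as serious. Section 8.3 lists stigma, discrimination and physical harm among the consequences of disclosure. It also accepts that FGD members may repeat comments or reveal who took part. Section 8.2 says that forms are read aloud because illiteracy is common, so participants rely on what staff say. The qualifier would also describe an HIV-negative partner in the group as HIV-positive.

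**Working it through.** The plan gives no figure to reproduce. The check is a comparison of texts and a head count.

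**Step 1: is the qualifier implied by any rule?**

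| Source | What it fixes about the non-index partner's HIV status |
|---|---|
| Section 3.1, criterion 3 | Nothing; the treatment requirement is for the index patient |
| Section 8.3 | Nothing; one HIV-positive partner is enough |
| Section 8.3.1 | Treats two positive partners as one possible case, so couples with one are foreseen |
| Section 5.13 | Tests only those who report HIV, so a partner who reports none is neither tested nor excluded |
| Sections 3.2 and 5.1 (FGD recruitment) | Partner must be interested and eligible; no HIV criterion added |

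No row makes the qualifier true. Section 2.2 refers to couples living with HIV, but that describes the target population and is not an entry criterion. Section 5.13 does not say whether its testing rule covers Aim 1. If it does not, the documents offer even less confirmation of status in the FGDs.

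**Step 2: how many people could the qualifier misdescribe?**

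Inputs are 2 couple FGDs with k = 3 to 4 couples each (Sections 3.2 and 5.1).

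- Members per group: 2k = 6 to 8. Over two groups: 2 × (6 to 8) = 12 to 16.
- Index patients, who must be living with HIV: k = 3 to 4 per group, or 2 × (3 to 4) = 6 to 8 in all.
- Members with no HIV requirement: 12 − 6 = 6 up to 16 − 8 = 8.
- Possible share HIV-negative or of unknown status: from 0 (every couple has two positive partners) to k / 2k = 50% (no couple does).

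**Step 3: what is the added exposure for one index patient?**

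The patient's own partner already knows, because Section 8.3.1 counts disclosure only if the partner verifies it. The added exposure is to the other k − 1 couples, that is 2(k − 1) = 4 to 6 people. Of these, k − 1 = 2 to 3 are other couples' index patients, who are living with HIV, and 2 to 3 are partners whose status no rule fixes.

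**Step 4: the stakeholder groups.**

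The three stakeholder FGDs hold 3 × (6 to 8) = 18 to 24 people chosen by role, with no HIV criterion. The sentence in Section 8.2 refers to the FGDs without distinction, so read literally it covers these groups too. They meet separately from the couples, so they add nothing to the counts in Steps 2 and 3.

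**The case against.** **What participants are told is not known.** The FGD consent form is separate and is not in the documents available for review. The qualifier could be an aside to the ethics reader and not part of the script. A reader might infer that people agree to disclosure on a false assurance. The documents do not show that; they show only a protocol description that conflicts with the eligibility text. Still, the qualifier sits inside the clause on what respondents will be told, so reading it as content to be conveyed is natural. Even as an aside, it gives the ethics committees an unsupported account of who is in the room.

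**Safeguards already exist.** The same sentence says that others will learn one's status and that confidentiality is not assured. Section 8.3 (loss of privacy) adds that FGD confidentiality risks are discussed at consent and that participants are asked to speak about people like them and not about themselves. This stands and lowers the stakes. It does not make the qualifier correct, and attendance as an index patient can reveal status whatever is said.

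**The qualifier may reflect an unstated restriction.** Section 8.2 is the only place that describes the HIV composition of the groups, and the team may have meant to convene only couples with two positive partners. This is possible, and it is why two repairs are open. If that was the intention, the recruitment text does not say so.

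**Stakeholders.** A reader might infer that HIV-negative stakeholders widen couples' exposure. They do not, because they are in different groups. All that remains is that the sentence does not say which FGDs it covers.

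**Conclusion.** The point holds as an internal inconsistency. The description of FGD consent in Section 8.2 is not supported by Sections 3.1, 3.2, 5.1, 5.13, 8.3 and 8.3.1.

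Its reach is two couple groups and 12 to 16 people, each seen once for Aim 1 (Section 3.3). The share who could be HIV-negative or of unknown status lies between 0 and one half. The upper end assumes that no couple in the groups has two partners living with HIV. The documents give no figure on this, so it would be wrong to read the upper end as the expected share.

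The consequence is conditional: if the qualifier is used as described, it understates the risk of disclosure to other couples' partners, in part offset by the warnings already present. The conclusion assumes that the Section 3.1 criteria govern FGD couples as well as trial couples; no separate FGD criteria are given. The trial's randomization, outcomes and analysis are not affected. Because the subject is informed consent on a risk the protocol itself names, and the correction is small, it should be made.

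**What to change.** Reconcile the passages in one of two ways.

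1. **Correct the consent description.** Delete the qualifier from Section 8.2 and from the FGD consent form if it appears there. State that group members may include people who are not living with HIV. Keep the existing statements that others will learn one's status and that confidentiality is not guaranteed; changing the first to say that others may learn it would weaken the warning.
2. **Make the description true.** Write into FGD eligibility (Sections 3.2 and 5.1) that both partners must be HIV-positive, and say how this is confirmed.

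Under either option, state that the HIV-status wording applies to the couple FGDs only, and give the stakeholder FGDs their own text. If the FGDs have already been held, check the wording that was actually used.

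The first option costs about one sentence and a wording amendment at the two ethics committees; a few people may decline. The second also needs an amendment and narrows FGD recruitment, leaving out couples with one HIV-positive partner, who remain eligible for the trial that the FGDs are meant to inform.

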8.3 Risks

This study is considered minimal risk. However, participation requires at least one partner to be HIV+ and thus respondents may be identifiable to others in the community by their participation in the study. The risks associated with knowledge of a respondent's HIV+ status in the community include social stigma (e.g., rejection, isolation) and discrimination (e.g., loss of employment or status in the community). The potential risks of the study can be grouped into five categories: 1) loss of confidentiality; 2) loss of privacy; 3) couple tension, conflict and/or violence, and coercion; 4) discomfort or distress as a result of the personal and sensitive nature of the interviews or intervention sessions on alcohol, relationship dynamics, and violence; 5)

Couple-Based Motivational Interviewing with Mobile Breathalyzers to Reduce Alcohol Use in South Africa

risks associated with finger pricks to collect blood samples for viral load and alcohol biomarkers (PEth); and 6) risk of COVID-19 infection.

The intervention may not be appropriate for couples experiencing severe current IPV. We will exclude couples in which one or both members report concerns about their safety or report experiencing or perpetrating severe IPV in the prior 3 months. IPV measures will be adapted WHO measure for South Africa, which assesses physical, sexual, and emotional violence, and determines whether it is mild, moderate or severe. This approach was chosen to minimize exacerbation of potentially volatile situations while participating in a relationship-focused intervention. Given that we are not excluding couples based on ever experiencing severe IPV, and including those couples reporting any mild- to moderate IPV, we believe that this balances sample generalizability with participant safety.

Loss of confidentiality. The loss of confidentiality may lead to disclosure of HIV infection and alcohol use disorder. Stigma associated with disclosure may include social harms such as discrimination (e.g., lost of employment or status in the community), physical harm (e.g., acts of violence being committed against people who have HIV), and psychological harm such as embarrassment (e.g., being questioned by family members about alcohol use). To protect participants' confidentiality the following steps will be taken: 1) all staff will receive training at the initiation of the study and ongoing supervision to ensure their understanding of any and all confidentiality-protecting procedures; 2) participants' names will not be associated with any research instruments; 3) only research identification numbers will be used on data; 4) any tracing or other contact information, including signed consent forms will be stored separately from the data; 5) all records will be stored in locked file cabinets in study offices at HRSC; 6) the files linking research identification numbers and names will be stored in a separate locked file cabinet, and a computer file only accessible by the Research Manager, PI and Co-Is; 7) all computers/tablets/phones on which any data are stored will be password protected.

As this is a study involving couples, additional measures are needed to protect each participant's confidentiality from their partner. From our prior work, we have developed procedures to minimize risk. For the study assessment interviews, all participants will be interviewed by a gender-matched interviewer who will conduct the interview in a private room. Couples will arrive together but be consented and interviewed separately. Prior to their separation, study staff will inform them that they may contact the staff member who interviewed them, but they will not be permitted to have contact with the interviewer who administered the survey to their partner. This procedure will enhance the participants' confidence that the information they disclose will be kept confidential and not disclosed to their partner. Each study staff member will only interact with one participant, and the interviewers will be instructed not to compare answers between them regarding a couple's answers.

The consent form will include specific language regarding the confidentiality of the partner's study data: "Please be aware that you will not be told any information that your partner says in his or her interview. This includes any information your partner might say about his or her health, even if we think you do not know this information. Likewise, no information you say in your interview will be told to your partner, even if we think your partner might not know this information." Interviewers will be trained to ensure that participants understand this condition during the informed consent process, including information about the confidentiality of their own

Couple-Based Motivational Interviewing with Mobile Breathalyzers to Reduce Alcohol Use in South Africa

and their partner's data. As mentioned above, systematically providing this information will eliminate partner's surmising that it is being provided due to information disclosed during the interview. It is possible that partners might ask each other about their responses to certain questions or issues discussed. Interviewers will be trained to discuss with participants ways of coping with this situation.

Loss of privacy. We will screen and interview couples in private locations and will take additional measures to protect respondents' HIV+ status. Although most activities will take place in the HIV clinics or other central community-based location, it will be important that interviewers maintain respondents' privacy if visiting the communities of respondents. To protect individuals' privacy, we will utilize language such as "Healthy Living" rather than referring to HIV or alcohol use when discussing the study.

There is the potential for additional privacy risks related to use of the breathalyzers in public, which could be stigmatizing if others in the community learn about their association with an HIV and alcohol study. When training participants on how to use the technologies for the study, we will counsel participants on how to best respond to questions from others on the breathalyzers and strategies to maximize privacy (e.g., finding a private space at drinking establishments to record BAC levels). During the consent process, we will explain these risks to participants to ensure they feel comfortable using the breathalyzers in the public space and participating in the study. We will provide a pouch to cover the breathalyzer and a phone cover to disguise the phone brand so these devices are not identifiable to the community and linked to the study.

During the FGDs which also utilize a group format, we will take additional measures to protect privacy. We will discuss the risks to confidentiality due to participating in FGDs in the informed consent processes. We will emphasize the fact that comments made during FGD sessions are to be kept confidential. However, it is possible that participants may repeat comments made or heard during FGDs in a different context in the future. They may also disclose the identity of other participants in the group. We will ask participants to not to talk specifically about themselves, but more generally about people they know who are like them or live in their communities. Although personal information and experiences may be discussed, the FGDs will primarily serve to obtain opinions on the proposed health intervention. The FGDs will be conducted in English/isiZulu by trained qualitative researchers with extensive experience in ensuring the safe conduct of group discussions. As with the interviews and survey, respondents will have the right at any time to decide not to participate or answer questions.

Couple tension, conflict, and/or violence, and coercion. It will be communicated in the consent form that while study staff members will not reveal participant information to their partner, it is possible that their partners might ask them about their responses to certain questions or issues they discussed. Interviewers will be trained to discuss with participants' ways of coping with this situation if the participant expresses concern or distress about this matter during consent, the administration of the survey, or after it is completed.

Although we have not had problems in the past in South Africa with participants reporting coercion, staff members will be trained to be sensitive to the possibility that one member of the couple was pressured or coerced by the other partner to participate in the study. Questions may be posed such as "Did you come here freely?" or "Will something bad happen to you if you say

Couple-Based Motivational Interviewing with Mobile Breathalyzers to Reduce Alcohol Use in South Africa

no?" Should the staff member have this suspicion, s/he will be trained to immediately terminate the survey or session and provide the participant with appropriate referrals and the study incentive. Any data collected will be destroyed. The staff member will also be trained to offer the participant the opportunity to remain in the interview room for the appropriate amount of time that it would have taken to complete the survey or interview so that the study partner would not be alerted to the fact that the interview was terminated. If necessary, back-up staff members who are clinicians can be contacted to assess the appropriate immediate steps, should intervention be needed. Should evidence of coercion/violence arise in the intervention sessions, assessment visits, or exit interviews, the counselor will provide the appropriate clinical intervention regarding participation of the couple, including assessing the level of safety and whether immediate medical/psychological attention is needed, and/or provide community referrals. Depending on the situation, procedures as described above will be followed in terms of determining next appropriate steps.

Interviewers and other intervention staff will also be trained in the identification of, and proper response to, issues of coercion or abuse, and will be familiar with how to facilitate referrals for intimate partner violence assistance (either for the violent partner or the victimized partner). For example, staff will assess the degree of threat, whether the participant's life is currently at risk, or whether the crisis is not of an imminent nature. Depending on the degree of threat, the participant could be referred immediately to a district crisis center, or, in lesser threat situations, could be provided with referrals for community-based services.

As stated in the inclusion criteria, couples will be excluded if they report a history of severe intimate partner violence in the past three months or feel their safety would be at risk. We do not wish to exclude a lifetime experience of violence from our sample, as that would potentially exclude participants who could benefit the most from the alcohol intervention. By screening out recent episodes (past three months) of severe intimate partner violence and/or women who feel their safety could be jeopardized by participation, we aim to have a sample that balances potential benefit with relatively low risk from a couples-based intervention. Incident risk for IPV will be assessed at all follow-up visits and intervention sessions. If IPV is reported during these visits, we will follow an established protocol to document the situation, assess safety for the partner(s), provide emotional support, and appropriate intervention and/or linkage to psychological and/or medical services.

We will also use a combination of actively and passive monitoring for violence during the intervention sessions and while the couples are independently using the breathalyzer devices. For active monitoring, a designated technology navigator will routinely check in with participants (separately with each partner) to ensure compliance and to troubleshoot any technical issues with using the breathalyzers/phones and will discretely monitor for violence. For passive monitoring, the technology navigator or another staff member at HSRC will be paired to participants and will be available to be contacted via phone should a safety issue arise during the study period. If a violence or safety concern is reported, the staff member will follow an established protocol to assess the degree of threat, whether the participant's life is currently at risk, or whether the crisis is not of an imminent nature. Depending on the degree of threat, the participant could be referred

Couple-Based Motivational Interviewing with Mobile Breathalyzers to Reduce Alcohol Use in South Africa

immediately to a district crisis center, or, in lesser threat situations, could be provided with referrals for community-based services.

Should a participant specifically request an IPV referral during a study visit, the staff member will immediately terminate the interview, provide the participant with the study reimbursement, offer to let the participant remain in the interview room for the approximate time of completion, and the assessment protocol for determining participant safety will be triggered. In addition, our resource list given to all participants will include intimate partner violence programs, clinicians, and support groups specializing in relationship abuse and violence.

Discomfort/distress. There could be some discomfort with the sensitive nature of the interviews on topics including alcohol use and couple conflict. Interviewers and study staff will be trained to minimize distress/discomfort to respondents, to recognize any signs of distress, and to make appropriate referrals to community-based services, if necessary. Our research team has a significant amount of experience conducting behavioral surveys and interviews within the field of HIV prevention and treatment, and with couples, including in the proposed setting. It has been our experience that it is rare for a participant to find the interview upsetting. We have infrequently encountered episodes of mild embarrassment or awkwardness, which quickly dissipate. Experienced lay counselors will be available on the study staff for consultations or referrals, should a respondent exhibit severe symptoms of mental distress. All couples' counseling sessions will be conducted by lay counselors, but who have received significant training pertaining to couples, so any distress during an intervention session will be able to be processed and dealt with appropriately. All staff will be trained in the proper referral procedures, and will be provided with ongoing supervision of such issues by the Research Manager. Through our work in this community, we have compiled a list of community-based resources, including mental health counseling, general health services, domestic violence, and substance use. This list of referrals will be continually updated, and systematically provided to every individual at every visit, which will reduce the likelihood that any one couple or individual would be identified as needing a particular service. Informed consent documents will inform research participants of potential discomfort around certain interview topics and the option to refuse to answer or skip any questions on the surveys that they are uncomfortable answering.

Blood draw injury. Viral load and PEth tests require participants to provide a blood sample through finger pricks. The physical risks associated with finger pricks are low, but could include pain and rarely, bruising and/or infection. All study staff will be cross-trained in how to collect DBS samples and in good clinical practice (GCP). GCP protocols will be followed for the handling and storage of DBS samples. Research assistants will report any complications resulting from the blood collection to the field study coordinator, who will make an immediate report to the local and UCSF PIs. The PIs will take responsibility for reporting serious adverse events to the IRBs.

Procedures for handling alcohol dependency. This is a pilot study of a behavioral intervention to reduce customary levels of alcohol consumption. Study staff will be clear in instructing participants not to drink alcohol in excess of their customary amounts such that study participation does not incur any increased risk above that of their customary alcohol consumption. Control arm participants will receive brief advice on alcohol use as part of the enhanced care control condition. However, our screening and follow-up visits may uncover

Couple-Based Motivational Interviewing with Mobile Breathalyzers to Reduce Alcohol Use in South Africa

